Background: Weight loss is important to improve overall health and reduce risk of obesity-related comorbidities such as diabetes. Most effective weight loss methods require a reduction in calorie intake. Some individuals with obesity find it more difficult to lose weight than others, due to inter-individual variation of resting metabolic rate and physical inactivity. Furthermore, individuals with predisposed genetic propensity to obesity who are deemed to be metabolically 'thrifty', require further structured intensification of lifestyle changes. Resting metabolic rate and respiratory quotient have proven to be effective predictors of weight loss.

Aims: This study aims to investigate whether providing energy expenditure information to patients and clinicians during a standardized multicomponent weight management intervention would influence the outcome of weight loss.

Methods: Participants recruited from the University Hospital Aintree weight management clinics, will be subsequently randomised to receive either 1) standard care (SC) - standard multicomponent weight management intervention (diet, exercise, behaviour modification therapy) or 2) intervention group (ECAL) – SC plus use of energy expenditure information to both clinicians and participants to influence dietary advice provided over a 6-month period. Primary outcome measure is the magnitude of weight loss. 7-day food diary used to establish compliance and MET average physical activity scores will be recorded.

This study will adhere to the principles outlined in the UK Policy Framework for Health and Social Care Research (v3.2 10th October 2017). It will be conducted in compliance with the protocol, the Data Protection Act, and other regulatory requirements as appropriate.

GLOSSARY OF ABBREVIATIONS

AE	Adverse Events
BMI	Body Mass Index
BP	Blood Pressure
BPI-SF	Brief Pain Inventory short form
CRF	Case Report Form
CI	Chief Investigator
DN4	Douleur Neuropathique 4
ECAL	Intervention Group
eGFR	Estimated glomerular filtration rate
EQ-5D	European Quality of Life – 5 Dimensions
FBC	Full blood count
HbA1c	Glycated haemoglobin
HDL	High Density Lipoprotein
HRA	Health Research Authority
IC	Indirect calorimetry
IWQoL-Lite	Impact of Weight on Quality of Life - Lite
KOSC	King's Obesity Staging Criteria
LFT	Liver Function Test
LDL	Low Density Lipoprotein
mTCNS	modified Toronto Clinical Neuropathy score
MT	Meal test
NEFA	Non-Esterified Fatty Acids
OSA	Obstructive sleep apnoea
PI	Principal Investigator
QoL	Quality of life
REC	Research Ethics Committee
REE	Resting energy expenditure
RMR	Resting metabolic rate
RQ	Respiratory quotient
SAE	Serious adverse event
SAR	Serious adverse reaction
SC	Standard care group
SOP	Standard operating procedure
SUSAR	Serious unexpected suspected adverse reaction
TFT	Thyroid function test
T2DM	Type 2 Diabetes Mellitus
U+Es	Urea, creatinine and electrolytes
UAR	Unexpected adverse reaction
VAS	Visual analogue scale for pain
WL	Weight loss

KEYWORDS

Weight management; Obesity; Complex Obesity; Diet; Structured dietary intervention; Calorie restriction; Indirect Calorimetry; Resting Energy Expenditure; Resting Metabolic Rate; Respiratory Quotient; Substrate oxidation; Macronutrient composition; Weight loss predictor; Peripheral neuropathy

SYNOPSIS

Study Title	A Randomized, Controlled Trial to Evaluate Impact of E nergy Expenditure Information from ECAL Indirect C alorimeter on the Outcome of Weight L oss during a Standardised Multicomponent Weight Management Intervention in Non-diabetic & Pre-diabetic Obese Subjects (ECAL study)
Study Setting	The study will be co-ordinated by the appointed research & development team based at University Hospital Aintree. The Liverpool Clinical Trials unit will provide trial management, statistical input, and database management for this trial. The study will include patients attending Weight Management Clinics at University Hospital Aintree.
Trial Design	A 24-week randomised controlled trial for subjects with obesity referred to a specialist weight management service. Participants will be randomised to receive 1) standard care (SC) control group receiving multicomponent weight management intervention (diet, exercise, and behaviour modification therapy), or 2) intervention group (ECAL) energy expenditure information via indirect calorimetry to guide the multicomponent weight management intervention. The aim of this study is to establish whether providing energy expenditure information to both clinician and patient from indirect calorimetry would influence the outcome of weight loss.
Trial Participants	All eligible patients currently attending specialist weight management services at University Hospital Aintree.

1. Introduction

Recent figures in 2016 demonstrated that over a 1 in 4 adults in England were obese, with a body mass index (BMI) of 30 kg/m² or higher(1). A further 41% of men and 31% of women were overweight, with a BMI of at least 25 but less than 30 kg/m²(1). Obesity is a multifactorial condition which results from chronic accumulation of fat in adipose tissue, which may stem from excessive energy intake, and or changes in body energy expenditure, resulting in a positive energy balance. The total amount of daily energy required to maintain normal bodily function including growth, repair of tissues and metabolic function is known as the basal metabolic rate (BMR). The BMR is the amount of calories (kcal or kJ) required to perform the body's basic metabolic function, most accurately measured in the lab settings. In contrast, the resting metabolic rate (RMR) is measured in a resting state, in the morning before any food, without any physical activity and after several hours of restful sleep overnight. Although the terms BMR and RMR are used interchangeably, the term resting metabolic rate is more commonly used. The RMR is calculated through application of the first law of thermodynamics and the Weir's formula. Using the principles from the first law of thermodynamics and Weir's formula, the simplified Weir formula(2) states that:

$$\text{Resting Metabolic Rate (kcal per day)} = 1.44 \times (3.94 \text{ VO}_2 + 1.106 \text{ VCO}_2) - 2.17 \text{ UN}$$

Where VO₂ is oxygen consumption in millilitres per minute and VCO₂ is the rate of carbon dioxide production in millilitres per minute. Indirect calorimetry allows capture of the exhaled gas using a face mask or mouthpiece connected to oxygen and carbon dioxide analysers.

The total daily energy expenditure (TDEE) is an estimation of how much calories an individual burn per day, taking into account the amount of calories burned through physical activity. TDEE is measured by multiplying BMR with the factor of physical activity level (PAL). The physical activity level is estimated using a sum of all physical activities (sum of Δ PAL) within a 24-hour period, hence: TDEE = BMR x factor of physical activity level (PAL). The role of physical activity is equally important as energy restriction in inducing and maintaining weight loss (3).

Accurate determination of BMR is possible using validated techniques in clinical trials in the research setting (4). Furthermore, indirect calorimetry has also been validated through comparison with BMR calculated based on predictive equations like Harris-Benedict equation (5).

1.1 Rationale for study

Das et al. (2004) prospectively measured total energy expenditure (TEE) and resting energy expenditure (REE) in extremely obese individuals and established that these individuals have high absolute values for TEE and REE, indicating that excess energy intake contributes to the maintenance of excess weight (6). However, Melo et al. (2008) found that obese individuals are economical, from the metabolic point of view (7). Therefore, the energy expenditure (EE) per kilogram of body weight at the given time is lower in obese individuals. Lam and Ravussin (2017) went on further to demonstrate complexity of the energy expenditure equation suggesting the variations between individuals and underlined the hypothesised concept of the 'thrifty' versus 'spendthrift' phenotypes(8). In theory, the thrifty individuals are more metabolically energy-conserving and thus are prone to weight gain.

1.2.1 Current Research on Energy Expenditure

TDEE calculated via predictive equations in obese hospitalised patients were only accurate in about half of patients, and tend to overestimate EE (9, 10). Nutrition and energy advice on critically ill (11), hospitalised patients or those in a hypocaloric state (12) are increasingly reliant on the accuracy of indirect calorimetry. Limited experience and technical variabilities of indirect calorimetry use in obese and severely obese individuals require further development and exploration (13, 14). Measurement of EE serves as an important component of comprehensive clinical nutrition assessment in institutions providing weight management interventions for obese patients. The hypothesis in this study is to examine whether utilising an indirect calorimeter to provide RMR and RQ would help obese patients to lose and maintain their weight loss.

1.2.2 Current Research on Respiratory Quotient

A prospective study of morbidly obese subjects with a BMI $\geq 35\text{kg/m}^2$ with a predisposition to weight gain subsequent to the cessation of a conventional rapid-weight-loss-diet or a very low-calorie diet were assessed during a 12-month follow up (15). A significant predictor for maintenance of weight loss in morbidly obese individuals was the observed differences in their resting RQ. The individuals who demonstrated an RQ in the lower range (<0.72) were more able to maintain the weight-loss achieved on a caloric restriction and avoid a weight loss rebound as compared to those with RQ in the higher range (>0.75)(16). This suggested that RQ could prove useful in clinical practice as a prognostic marker for long-term effectiveness of low- and very-low-calorie diets used to induce rapid weight loss. The Baltimore Longitudinal Study on Aging shared a similar finding that fasting RQ or respiratory exchange ratio (RER) adjusted for age, BMI, FFM was positively related to weight change(17).(18)

1.2.3 Current Research on Resting Metabolic Rate

Fat free mass (FFM) which represents numerous metabolically active tissues (skin, bone, muscle) and organs (heart, liver, kidney, brain) is thought to be a major determinant of energy expenditure and fat utilization in lean healthy individuals. Resting metabolic rate (RMR) adjusted for fat free mass (FFM) was a predictor for change in body weight, with studies demonstrating RMR is inversely related to rate of weight gain(19). Two further studies by Piaggi et al. (2013, 2015) supports that 24-hour EE was inversely related to rate of weight gain, and further demonstrated that a higher 24-hour RQ and EE, but not FFM, were independent predictors of ad libitum food intake(15, 20). Similarly, a study on ethnic Pima Indians with high prevalence of obesity demonstrated a low RMR was a significant risk factor for weight gain(21). Further evaluation of this suggestion of a “Thrifty genotype” amongst this population, with obesity prevalence that exceeds 75%, led to the conclusion that a low RMR is predictive of overall weight gain(21). Another study comparing the RMR of 10-year old Pima Children with Caucasian cohorts found that RMR adjusted for body composition and FFM was not significantly different(22). However, other studies report no significant association was found between RMR and weight gain in obese individuals(17, 23).

1.3.1 Definition of Prediabetes

Prediabetes is diagnosed when:

- **Glycated haemoglobin (HbA1c)** 42 - 47 mmol/mol (24)
- **Impaired Fasting Glucose** - Fasting blood glucose level of (5.5 mmol/L to 6.9 mmol/L) and / or
- **Impaired Glucose Regulation** - Two-hour glucose tolerance test after ingesting the standardized 75 g glucose meal to the blood sugar level of 7.8 – 11.0 mmol/L and / or

We defined prediabetes among individuals without previously diagnosed diabetes using HbA1c cut-offs as specified by the NICE(24) . This cut-off has been shown in a meta-analysis to be predictive of progression to diabetes. Patients who had a previous diagnosis of diabetes were excluded because the current glycaemic status of those patients may represent diabetes control. The levels above these readings would be a diagnosis for diabetes.

Prevalence of prediabetes is on the sharp increase from 11.6% to 35.3% from comparative surveys in 2003 to 2011(25), while about 1 in 10 individuals with prediabetes progress to develop diabetes every year (26).

1.3.3 Peripheral neuropathy and Prediabetes

A prospective Canadian study demonstrated that individuals with prediabetes carries a similar risk of peripheral neuropathy as new-onset type 2 diabetes in people around 50 years of age(27). Patients with at least one or more risk factors of developing type 2 diabetes were monitored over a 3-year period. Results of PROMISE trial showed that over the course of the 3-year monitoring period, 50% of participants had peripheral neuropathy(27). Of those that developed prediabetes (either impaired fasting glycaemia or impaired glucose tolerance), 49% also had peripheral neuropathy. By comparison, of those participants that maintained healthy blood glucose levels, 29% had peripheral neuropathy.

The results outline that people with prediabetes are at a higher risk of peripheral neuropathy than the general population and that monitoring for signs of nerve damage should be carried out to reduce the risk of foot damage and potential consequences that can result.

1.4 Substrate oxidation

Obesity is associated with impaired glucose tolerance and impaired utilisation of fat as a fuel during post-absorptive conditions(28). The proposed mechanism of impaired glucose tolerance, which is due in part to increased availability of plasma free fatty acids (FFA) and reduced capacity of skeletal muscle fat utilization (28, 29), leading to accumulation of intracellular fatty acid metabolites that interfere with insulin signalling pathways(30, 31). In lean metabolically healthy individuals, measurement of the RQ reveals a higher reliance on fat oxidation (lower RQ) during fasting conditions. Insulin infusion in these individuals readily suppresses this preference of fat oxidation as muscle shifts to higher reliance upon glucose oxidation (higher RQ). Thus metabolically healthy skeletal muscle is characterised by the ability to switch easily between glucose and fat oxidation in response to homeostatic signals. In comparison, the skeletal muscles of obese individuals and type 2 DM demonstrate a great reduction in this metabolic flexibility. RQ values measured in a fasted state are elevated in obese and type 2 DM individuals (32), yet the stimulation of glucose oxidation in response to insulin is blunted. This blunted capacity and inefficient response to both to the stimulus of fasting to enhanced fat oxidation and to the stimulus of glucose oxidation in response to insulin, is termed “metabolic inflexibility”.

1.5 Proposed research

Indirect calorimetry has been extensively used in both research and clinical setting in lean and healthy individuals, with lack of congruent results on individuals with complex obesity. This study aims to explore the use of indirect calorimetry to provide energy expenditure information to clinicians and patients during a 6-month standardised multicomponent weight management intervention.

Research Question:

- Does providing energy expenditure information to both clinicians and patients during weight intervention influence the outcome of weight loss?

2 Study objectives

2.1 Primary Objective

- To determine whether providing energy expenditure information from indirect calorimetry to specialist clinicians and patients influences the outcome of weight loss in patients with obesity and severe obesity.

2.2 Secondary Objectives

1. To establish the acceptability and reproducibility of using indirect calorimetry to measure energy expenditure as compared to use of standard predictive energy equations.
2. To determine whether metabolic parameters of REE or RQ are potential surrogate biomarkers to predict weight loss.

3 Study design

Type of study: Randomized-controlled trial

Primary endpoint

Reduction in body weight from baseline to end-of treatment (24 weeks)

4. Study population

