5.2 Baseline visit & Randomisation

Eligible participants will be able to proceed to the Baseline Visit (Week 0). Weight, blood pressure and pulse rate will be recorded for all patients in line with study SOPs. The patient will also complete questionnaires to provide demographic and medical history details and additional data will be collected. Participants will be counselled about the study visits and provided with a food diary to record their food intake during the week. Participants will each receive support from the dieticians and weight management practitioners and/or clinicians with regards to maintaining reduced calorie intake according to their respective groups. Participants may contact their study team or GP at any time.

Eligible participants will then be randomly assigned to one of two groups in a 1:1 ratio:

- 1) The *control group* (SC) – standard care including diet, exercise and behaviour modification therapy. Energy expenditure information (RMR, RQ) measured from IC will be **withheld** from participants until the final visit. Participants will receive a standard nutritional energy goal based on the Harris-Benedict equation, the standard predictive equation used at Tier 3 weight management service at Aintree University

Hospital. Both participants and the study clinician providing advice and care will be “blinded” to the client and practitioner report until the completion of the final visit (week 24). To maintain the “blinding” of both participant and clinician in the SC group, the IC measurement is performed and an electronic copy of this is stored in the database, without showing the report to the participant or clinician. Upon completion of the final visit, SC group participants will be able to request a copy of the relevant client reports, should they wish to do so.

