5.4 Standard Care Group Clinical Visits

(weeks 1, 2, 4, 8, 12, 16, 20 and 24)

Standard Care (SC) group participants will receive IC testing at baseline (week 0), week 1, 2, 4, 8, 12, 16, 20 and week 24, but energy expenditure information is **withheld** from the patient until the final visit. Participants would receive a standard nutritional energy goal based on standard predictive equations. At the final visit (week 24), a summary of their energy expenditure (RMR, RQ) information will be provided and presented as a layperson print out.

SC group participants will continue to receive diet, exercise and behavior modification therapy as a standard multicomponent weight management intervention as part of their weight management service.

5.5 - ECAL Group Clinical Visits

(week 1, 2, 4, 8, 12, 16, 20 and 24)

In addition to the multicomponent weight management intervention (diet, exercise and behavior modification therapy), ECAL group participants will receive energy expenditure information measured from IC.

ECAL group participants will receive IC testing at baseline (week 0), week 1, 2, 4, 8, 12, 16, 20 and week 24. RMR measured from IC test will be proven to be more accurate and less variable than standard predictive equations. REE will provide the basis of specific caloric restriction necessary for the individual to maintain their target weight loss. RQ will also be generated from the ratio of VCO_2/VO_2 which provides information about substrate oxidation, more specifically measured fat utilization over the past 24 hours. REE and RQ

information will be used to guide clinicians in recommending the appropriate caloric restriction and lifestyle changes to help promote active weight loss. Participants will receive verbal feedback and a layperson summary of the recommendations. The indirect calorimetry can also be used to demonstrate and compare the results of REE and RQ from previous weeks.

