Accordingly, one measure would be sufficient to measure the REE. However, if the operator cannot guarantee the stability of the readings, the combination of two or three repetitions would increase the precision of the measurements. In such instances, the average of the two best readings will be utilized. A designated and trained healthcare professional will be responsible to operate and check the accuracy of data collection from IC.

Energy expenditure (EE) information obtained from indirect calorimetry includes resting Energy Expenditure (REE) and respiratory quotient (RQ).

Measures to ensure safety relating to the current COVID-19 pandemic will be introduced as per government guidance at the time of the participant visit. At the time of writing, the following measures will be instigated: social distancing, use of protective face masks, and any appropriate personal protective equipment when social distancing not possible. One-way flow of participants and an assessment of any possible COVID-19 symptoms the day prior to attendance and day of attendance. If there are any symptoms, advice will be provided, and the visit rescheduled for a later date and advised to contact local healthcare service and undertake COVID-19 testing. Temperature will be assessed on arrival and if $\geq 37.8^{\circ}\text{C}$ then the visit will be rescheduled. Medical advice / testing will be performed if applicable.

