6.2 Statistical Analysis

Patient characteristics and clinical data will be analysed using SPSS software and STATS Direct. Normally distributed data will be expressed as mean +/- standard deviation (SD). Categorical variables will be analysed by using Chi-squared testing. Continuous variables between groups will be evaluated with unpaired student's t-test (if normal distribution) or Mann-Whitney U test (if not normally distributed). P values < 0.05 will be considered significant.

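### Secondary objective 1 sets the reproducibility of calorimetry against a fixed formula, and Section 5.5 announces a result on accuracy and variability that the design cannot show

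*Protocol*

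**What the plan says.** Protocol Section 2.2, secondary objective 1: "To establish the acceptability and reproducibility of using indirect calorimetry to measure energy expenditure as compared to use of standard predictive energy equations".

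Section 5.2 names the equation, for the control group: "Participants will receive a standard nutritional energy goal based on the Harris-Benedict equation".

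Section 5.5, describing the ECAL group visits, states: "RMR measured from IC test will be proven to be more accurate and less variable than standard predictive equations". No reference method for accuracy is named anywhere. Section 1 cites comparison with equations of the Harris-Benedict type as validation of calorimetry.

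On repeat readings, Section 5.9 says: "Accordingly, one measure would be sufficient to measure the REE". More are taken only on a condition: "if the operator cannot guarantee the stability of the readings, the combination of two or three repetitions would increase the precision of the measurements". In that case the two best readings are averaged.

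Both arms have calorimetry at week 0 and at weeks 1, 2, 4, 8, 12, 16, 20 and 24 (Sections 5.4 and 5.5). Acceptability is covered by a 7-question patient survey and a 10-question staff survey, both about calorimetry only (Section 5.10).

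**The concern.** Reproducibility is a property of a measurement: how far repeated readings in the same person differ when nothing has changed. A formula has no such property. The comparison in objective 1 is therefore settled before any data are collected, and in the direction opposite to the one Section 5.5 expects.

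The accuracy claim has a different fault. To call one of two methods more accurate, both must be judged against a third. Here calorimetry is the only measured value. If it serves as the reference, the conclusion is assumed. If the equation serves as the yardstick, as Section 1 implies, calorimetry cannot be shown to be better than it.

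At stake is a published statement that calorimetry was proven more accurate and less variable, resting on data that cannot support it. Section 1.5 itself says that results in complex obesity have not been consistent, so the question is open in this population.

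**Working it through.** **1. The protocol's own figure.** Section 4.4 gives SD 4.88 kg, difference 3 kg and power 80%; Section 6.2 gives alpha 0.05, taken as two-sided. n per group = 2 × (1.96 + 0.84)² × 4.88² / 3² = 2 × 7.85 × 23.81 / 9 = 41.5, so 42. The total is 84, and 84 / 0.80 = 105. The stated figures reproduce, and nothing below changes them.

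**2. Test-retest variability of the two methods.** For the formula, same inputs give the same output, so the within-subject SD is 0. (That Harris-Benedict is a fixed formula is general knowledge; the protocol does not print it.) For calorimetry the protocol gives no within-subject CV. The difference between two readings that is exceeded only 5% of the time is 1.96 × √2 × CV:

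| Assumed CV | Calorimetry | Formula |
|---|---|---|
| 3% | 8.3% | 0% |
| 5% | 13.9% | 0% |
| 10% | 27.7% | 0% |

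Any CV above zero gives the same ordering. The 10% limit in Section 5.9 is a within-test steady-state rule for VO₂ and VCO₂, not a test-retest figure, and is not used as one here.

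**3. Accuracy.** Write M for the measured value, E for the equation value and T for the true value. The claim concerns M − T against E − T. The trial observes M and E only, so it can estimate M − E, which is agreement. It cannot divide that difference between the two methods.

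**4. What the planned data can give.** Calorimetry is done at week 0 in everyone, height and weight are measured before the test (Section 5.9), and demographics are collected at baseline (Section 5.2). A pair (M, E) can be formed for each participant. With 105 pairs:
- Each limit of agreement has a 95% half-width of 1.96 × √(1/105 + 1.96²/(2 × 104)) = 1.96 × 0.167 = 0.33 SD of the differences.
- If half the predictions fall within 10% of measured (an illustration prompted by Section 1.2.1, which says equations were accurate in about half of obese inpatients), the 95% half-width is 1.96 × √(0.5 × 0.5 / 105) = 9.6 percentage points.

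**5. Repeatability of calorimetry alone.** There are no planned duplicates within a visit. Repeats are triggered by instability and then selected, so they do not estimate ordinary reading error. The closest pair in time is week 0 and week 1. With d the difference and δ any real change, s² = Σd²/(2n) estimates σ² + E(δ²)/2 if δ is independent of error. It therefore overstates σ² unless nothing changed. SC participants start diet, exercise and behaviour therapy at week 0, so δ cannot be taken as zero. With about 105 / 2 ≈ 52 SC pairs, the relative 95% half-width of s is about 1.96 / √(2 × 52) = 19%.

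**The case against.** The best reply is that less variable may mean person-to-person error rather than test-retest error. Section 1.2.1 supports this: it reports that equations missed in about half of obese inpatients and tended to overestimate. On that reading a formula does vary in its error. This is fair, but person-to-person error is still error against something. With calorimetry as the reference, its own error is zero by construction. The reading therefore supports an agreement analysis, not a proof of superiority.

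It can also be said that the Section 5.5 sentence is rationale in a visit description, with no endpoint or decision tied to it. That limits the harm, but the sentence still announces a result on the very comparison that objective 1 names. An analysis plan that is not shown could add methods; it would not change this wording.

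Two stronger readings are tempting and are not supported. A reader might infer from Section 6.2 that calorimetry and equation values from the same people will be compared with unpaired tests. The sentence begins "Continuous variables between groups will be evaluated with unpaired" and is limited to comparisons between groups. Nothing plans an unpaired test of one method against the other, and agreement methods are commonly left to the analysis plan. A reader might also infer that objective 1 cannot be answered at all. The surveys can describe the acceptability of calorimetry, although they cannot compare it with equations, and the paired values can be formed from planned data.

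**Conclusion.** The point holds for the reproducibility and accuracy comparison in Section 2.2 and for the sentence in Section 5.5. The first is ill-posed, because one side has zero test-retest error by definition. The second asserts a result that cannot be shown without an independent reference. This rests on Harris-Benedict being a fixed formula and on no reference method being named; it does not depend on the assumed CVs, which only illustrate scale.

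It concerns a secondary objective. The primary objective, the endpoint and the sample size are untouched. The change should be made because it is nearly free and prevents a foreseeable unsupported claim.

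**What to change.** Split objective 1 into three parts.

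- **(a) Acceptability of calorimetry**, described from the Section 5.10 surveys, with no comparison to equations.
- **(b) Agreement** between measured RMR and the Harris-Benedict resting value in the same person at week 0, both arms pooled: Bland-Altman bias and limits of agreement, plus the proportion of predictions within 10% of measured. Use the equation's resting value, not an energy goal derived from it.
- **(c) Repeatability of calorimetry alone**, as the within-subject SD from weeks 0 and 1 in SC, labelled an upper bound on device error because the intervention has started. State that it refers to the recorded visit value: repeats are taken only when readings are unstable and the two best are averaged, so it does not bound the error of a single unstable reading.

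In Section 5.5, delete the sentence that says superiority will be proven, or restate it as a hypothesis about agreement.

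The cost is wording in Sections 2.2 and 5.5 and a small analysis of data already planned. The trial gives up an accuracy claim that it could not have supported.
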